- Cognitive dysfunction which limits the ability of the participant to adequately understand procedures and risks.
- Prisoners

- Pregnant Women

Special populations:

- Adults unable to consent: excluded from study
- Individuals -who are not yet adults: individuals who are less than 18 years old will be excluded from the study
- Pregnant women: Women who are known to be pregnant will not be recruited into the study. A pregnancy test will be administered to females prior to enrollment in TENS (or sham) treatment. Women who become pregnant before or during the 8-week TENS treatment period will be discontinued from the study. Women who become pregnant after the 8-week TENS treatment portion of the study will continue to be enrolled, and followed according to protocol guidelines (no information will be collected specifically on the pregnancy or fetus).
- Prisoners: excluded from study
- Neonates: not applicable

5) Number of Subjects*

This is a single-site study and 98 potential participants with newly-acquired spinal cord injuries will be enrolled. See section 22, for more information.

6) Study-Wide Recruitment Methods*

This is not a multi-center study. See section 21.

7) Study Timelines*

It is anticipated that subjects will be enrolled in the study for 12 months (see **Figure 5**, in section 10, below, for procedures timeline).

It is anticipated that enrollment of subjects will occur between November 1, 2016 and January 1, 2022. This enrollment end date is 12-months prior to the end of the funding cycle for this grant, which will allow for complete follow-up of all subjects before study termination.

The estimated date for the investigators to complete this study is October, 2022.

8) Study Endpoints*

The primary study endpoints/outcomes are: 1.) the percentage of subjects who develop chronic neuropathic pain at the 12-month post-spinal cord injury time point (as defined by a score of ≥ 2 on the Spinal Cord Injury Pain Inventory (SCIPI), a self-report scale of symptoms); and 2.) the severity of chronic neuropathic pain (as measured by a self-report rating of neuropathic pain symptoms) measured at the 12-month post-spinal cord injury time point. The secondary study endpoints/outcomes include other aspects of pain symptoms and physical and emotional function. All outcomes and other variables are listed in Table 2 and described in detail below, within the “Procedures Involved” section.

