Assessments of primary and secondary outcome measures will occur at the time points

diagramed in Figure 5. Details regarding the specific assessment tools and measures to be used are described below and listed in **Table 2**. The primary outcome variables for Aim 1 (Spinal Cord Injury Pain Instrument (SCIPI)⁸⁰ score of ≥ 2 , and Neuropathic Pain Symptom Inventory score⁸⁹) will be collected during each scheduled assessment (full and abbreviated assessments), with additional outcome measures recorded less frequently (during full assessment sessions only: 4 times during the study).

Randomization and blinding procedures:

A blocked randomization procedure will be used, so that for each eight patients enrolled, four will be allocated to TENS and four to Sham TENS. A computer-generated random assignment sequence will only be accessible to the study staff member responsible for delivering TENS treatments. The PI of the study, the researchers evaluating pain diagnoses, and the research subject will not be informed of the treatment allocation assigned. All subjects will be told that they may or may not feel the stimulation from the TENS unit during treatment sessions due to the parameters of the study. The stimulation parameters of the TENS unit will not be visible to the subject, so that subjects will not obviously know to which study group they were randomized.

Treatment procedures:

(a) *TENS device*: The TENS 7000 Dual Channel battery-powered digital stimulator (Roscoe Medical, Ohio, USA) will be used. This device provides for adjustable frequency/pulse rate, pulse width, and amplitude, as well as recording of session data (settings and duration of treatment session). The TENS 7000 device has two channels. Each channel will be connected to two self-stick square electrodes (thus, a total of 4 electrode pads will be used) with dimensions of 2 inches by 2 inches. New electrode pads will be used for each treatment session.

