Based on a total sample size of 98 subjects, and an estimated 15% drop-out rate, we expect that approximately 82 subjects will complete the study (i.e., 41 subjects per treatment arm). Based on previous work,^{21, 59} we project that 60% of subjects in the Sham TENS (control) group will have at- or below-level neuropathic pain at the 12 month follow-up time point. Thus, with 41 subjects in each group, $\alpha = 0.05$, power of at least 80%, and an analysis based on a two-sided Z-test (for group difference in proportion of subjects with neuropathic pain) for *Hypothesis 1a*, we will be able to detect at least a 50% reduction in the rate of subjects with chronic neuropathic pain in the TENS treatment group compared to the Sham group at 12 months post-SCI (i.e., Sham TENS = 60% with neuropathic pain; Treatment TENS = 30% neuropathic pain).

For t-test analyses assessing differences between groups (Sham vs. Treatment) using continuous variables (e.g., NRS, NPSI), 41 subjects in each group will allow for detection of a medium-to-large effect size (i.e., Cohen's $d = 0.6$) with α set at 0.05 and power of 0.80. Paired correlations will also be used for additional analyses (*Aim 2*). For correlations within group ($n = 41$), with power set at 0.80 and $\alpha = 0.05$, we will be able to detect a medium-to-large effect size (i.e., Cohen's $f^2 = 0.20$), and we will be able to detect a small-to-medium effect size for across-group analyses ($n = 82$; Cohen's $f^2 = 0.10$).

Data analysis plan:

Descriptive evaluations of the data will be performed for all variables to check the integrity of the data and to verify the underlying assumptions of the statistical tests that are planned. If necessary, and as appropriate, data will be transformed prior to any parametric analyses, or non-parametric techniques will be used with untransformed data. Statistical analyses will use two-tailed tests and an a-priori α of 0.05.

In addition to direct tests of hypotheses (described in detail below), descriptive analyses and graphical representations (e.g., spaghetti plots) of data will be used to describe longitudinal

characteristics of clinical pain, somatosensory function, and other physical and psychological outcomes across the 12-month timeline of study participation.

Hypothesis 1a:

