The primary statistical analysis, to test the effectiveness of prophylactic TENS for neuropathic pain after SCI will be via a two-proportion z test, comparing the percentage of subjects in the TENS treatment group who are “positive” for neuropathic pain at 12 months post-injury to the percentage of subjects in the Sham TENS group who are positive for neuropathic pain at 12 months post-injury. Subjects who score a 2 or more on the SCIPPI for a pain located at or below their neurological level of injury at the 12 month follow-up time point will be considered positive for neuropathic pain. Subjects who do not have a pain at- or-below the level of injury or a score of 2 or more on the SCIPPI will be considered negative for neuropathic pain. For those subjects who have neuropathic pain symptoms early after injury (i.e., prior to entering the study), a “positive” result for neuropathic pain will be defined as having neuropathic pain that is moderate or greater (rated at least a 4 out of 10) at the 12 month follow-up assessment.

Additional analyses will be conducted using secondary outcomes collected at the 12-month time point: 1) comparison of pain severity (using the NRS and NPSI scores) between the groups (This analysis will be especially important if the primary analysis does not show a difference in rates of the presence of neuropathic pain at 12 months.); 2) comparison of use of analgesics between groups; and 3) comparison of response to pain interference questions from the ISCPBDS2. General linear model analyses will be used, with TENS group (Treatment vs. Sham) as a categorical predictor of these secondary outcome measures.

Separate analyses for at-level neuropathic pain and below-level neuropathic pain, as well as nociceptive pains, will also be conducted to examine whether TENS differentially impacts their development or severity. Additional analyses will be conducted, using the diagnosis of each pain type according to ISCPBDS guidelines, as determined and agreed upon by our study staff pain experts, as a confirmation of the primary neuropathic pain metric (SCIPPI ≥ 2).

Hypothesis 1b:

To investigate factors that may be related to patient responsiveness to TENS as a preventive treatment for chronic neuropathic pain, we will assess correlations between changes in evoked pain (before and after TENS treatments) and the presence and severity of neuropathic pain

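### Minor: with 41 per arm the severity t-test has 76.5% power at Cohen's d = 0.6, not the stated 0.80; 80% is reached at d = 0.63

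*Combined protocol and SAP*

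**What the plan says.** Section 11 (Data Management), under Power / sample size, starts from 98 enrolled and 15% drop-out, and says "we expect that approximately 82 subjects will complete the study", split as 41 per arm. For t-tests of Sham against Treatment on continuous variables it says that "41 subjects in each group will allow for detection of a medium-to-large effect size", which it puts at Cohen's d = 0.6, with alpha "set at 0.05 and power of 0.80". The data analysis plan that follows specifies two-tailed tests at alpha 0.05. No standard deviation, difference in scale points or second decimal of d is given.

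Section 8 (Study Endpoints) lists as its second primary endpoint "the severity of chronic neuropathic pain (as measured by a self-report rating of neuropathic pain symptoms" at 12 months. The Overview in section 9 names the SCIPI cutoff "and Neuropathic Pain Symptom Inventory score" as the primary outcome variables for Aim 1. Section 11, under Hypothesis 1a, places the severity comparison differently: "Additional analyses will be conducted using secondary outcomes collected at the 12-month time point", with NRS and NPSI severity first on the list and the remark "This analysis will be especially important if the primary analysis does not show a difference in rates of the presence of neuropathic pain". On the model it says: "General linear model analyses will be used, with TENS group (Treatment vs. Sham) as a categorical predictor". It names no covariate for this comparison.

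**The concern.** The sentence gives every input needed to check it: sample size per arm, effect size, alpha and power, with sidedness stated in the same section. A reader who enters n = 41 and d = 0.6 into a standard t-test power calculation does not get 0.80. Because this is the only power statement that covers the severity comparison, it is the plan's sole account of how sensitive that comparison is. What is at stake is the accuracy of that account: at d = 0.6 the chance of missing the effect is 23.5% (100 − 76.5), not 20%.

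**Working it through.** **Inputs, all from the plan.** n = 41 per arm, d = 0.6, alpha 0.05, stated power 0.80 (section 11, Power / sample size); two-tailed tests (section 11, Data analysis plan); 1:1 allocation (section 9, Randomization and blinding procedures).

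**Step 1: the plan's own figure.** Two-sample t-test, noncentral t distribution.
- Degrees of freedom = 41 + 41 − 2 = 80.
- Noncentrality = d × √(n/2) = 0.6 × √20.5 = 2.717.
- Two-sided critical value, t(0.975, 80 df) = 1.990.
- Power = P(|T| > 1.990 given noncentrality 2.717) = **76.5%**.
- Normal approximation: Φ(2.717 − 1.960) = Φ(0.757) = 77.5%.

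Neither method gives 80%.

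**Step 2: the effect detectable at 80% power with 41 per arm.**
- Noncentral t, solved for d: **0.626**. At d = 0.63, power is 80.5%.
- Normal approximation: (1.960 + 0.842) × √(2/41) = 0.619.

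Both become 0.6 at one decimal.

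**Step 3: whether another reading of the plan gives 80% at d = 0.6.**

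| Reading | Power at d = 0.6 | Remark |
|---|---|---|
| 41 per arm, two-sided | 76.5% | as stated |
| 42 per arm (98 × 0.85 = 83.3 completers) | 77.6% | 80% at d = 0.619 |
| 49 per arm (all 98, no drop-out) | 83.6% | the sentence says 41 |
| 41 per arm, one-sided 0.05 | 85.3% | the plan says two-tailed |

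Covariate adjustment could close the gap. It would need a correlation with the outcome of about √(1 − (0.6/0.626)²) ≈ 0.29, but no covariate is named for this comparison. The general linear model with treatment group as predictor is then the same test as the t-test.

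**Step 4: the other figures in the same section.**
- Correlations (noncentral F, 1 and n − 2 df, noncentrality f² × n): 79.7% at f² = 0.20 with n = 41, and 80.8% at f² = 0.10 with n = 82. The values of f² giving exactly 80% are 0.201 and 0.098, which match what is printed.
- Prevalence, 60% v 30% with 41 per arm: 79.0% by the pooled z formula, 81.3% by exact enumeration of the uncorrected z-test. This is consistent with the stated 80%.

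Only the t-test figure misses by more than about one point.

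**The case against.** The strongest reply is that the sentence is correct at its printed precision. Alpha and power are the inputs there and d is the output; the output is 0.626, and to one decimal that is 0.6. On that view the 76.5% appears only when a rounded result is put back in as if it were exact. The surrounding text is approximate as well: the completer count is an approximation, the effect is described only as medium-to-large, and the plan allows transformation or non-parametric methods, so t-test power is nominal for these outcomes in any case.

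Much of this stands. Rounding is the likeliest explanation, although the plan does not say so, and the four printed values can be reconciled by reading 0.6 as a one-decimal result. What remains is the direction of the rounding. A minimum detectable effect rounded down claims 80% power at an effect where the design does not have it. The correlation effect sizes in the same paragraph are printed to two decimals and come within 0.3 and 0.8 points of 80%; the t-test figure, given to one decimal, is 3.5 points away.

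A reader might infer more than this, and the documents do not support it.
- *That the trial is too small for severity.* Holding d = 0.6 at 80% would take 45 per arm (80.4%; 44 gives 79.5%), or 90/0.85 ≈ 106 enrolled. But the sample size is presented first through the prevalence comparison, and the plan never says that d = 0.6 is a threshold of clinical importance. A shift from 0.60 to 0.63 does not make the design inadequate.
- *That the plan ties the reading of a null severity result to this figure.* It calls the severity comparison especially important if prevalence shows no difference, but nowhere makes its interpretation depend on the power statement.
- *That the power section as a whole is unreliable.* The prevalence and correlation figures reproduce.

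**Conclusion.** Wrong as written, and minor. At d = 0.6 with 41 per arm and two-sided alpha 0.05, power is 76.5%, not 80%; the effect detectable at 80% is d = 0.626. The size of the slip is 3.5 percentage points of power, or 0.026 in d, and it makes the severity comparison look slightly more sensitive than it is. The result rests on an unadjusted two-sample t-test, 41 completers in each arm and d read as printed; the normal approximation and 42 per arm lead to the same conclusion. Conduct is unaffected: section 7 ends planned enrolment on January 1, 2022, and this version is dated July 18, 2022. The arithmetic is certain; the cause, probably rounding, is an inference.

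**What to change.** In section 11, Power / sample size, restate the sentence on continuous outcomes as: '41 subjects in each group give 80% power to detect Cohen's d = 0.63 (about 77% power at d = 0.6), two-sided alpha 0.05.'

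Leave the sample size, the endpoints, and the prevalence and correlation statements unchanged. The cost is one sentence, with no effect on visits or staff. The only downside is a slightly less favourable printed figure.

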- Neuropathic pain: pain caused by a lesion or disease of the somatosensory nervous system; typified by “burning,” and “electric” spontaneous pain, and may include allodynic or hyperalgesic responsiveness
- Nociceptive pain: pain that arises from actual or threatened damage to non-neural tissue and is due to the activation of nociceptors
- Spinothalamic tract (STT): the major ascending pathway for information about pain and temperature. Information from A δ and C fibers (which are activated by noxious stimuli) in the periphery travel to an anterior region of the spinal cord and ascend to brainstem, thalamus, and cortex via the spinothalamic tract.

Pain is defined by the International Association for the Study of Pain as “an unpleasant sensory and emotional experience associated with actual or potential tissue damage, or described in terms of such damage.”¹ *Acute pain* is time-limited by the inciting injury or disease and serves a protective function, while *chronic pain* is a persistent pain experience that outlasts the inciting injury and is thought to have limited biologic utility.² In some studies “chronic pain” is defined as pain persisting for at least three months, and in other studies is defined as pain persisting for at least six months. For the purpose of this proposal, we operationally define chronic neuropathic pain as neuropathic pain that has persisted for three months or more.

Pain taxonomies typically differentiate between two main types of pain: nociceptive and neuropathic. *Nociceptive pain* is pain that occurs in the intact nervous system and arises from normal activation of nociceptors, while *neuropathic pain* is defined as pain due to a nerve lesion. Neuropathic pain symptoms feature spontaneous pain (pain without stimulation) that is frequently described as burning, pricking, or electric-shock-like³ and that occurs in an area affected by a lesion of the somatosensory nervous system which results in negative (i.e.,

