Results from 50 people with chronic SCI (white, non-Hispanic = 9; white, Hispanic = 18; black, non-Hispanic = 21) who completed a phone survey using screening tools for neuropathic pain (SCIPI, ISCIPIBDS).⁵⁹

Figure 3: Persons with SCI and pain identify neuropathic pains as worse than non-neuropathic pains.

Data is from 29 subjects with chronic traumatic SCI who differentiated at least 2 pains. Neuropathic pain was more likely to be labeled as their worst pain than non-neuropathic pain ($p < 0.05$).⁵⁹

We have recently presented data⁵⁹ from a phone survey in people with chronic traumatic SCI (between 1 and 4 years post-injury) in which we used the International Spinal Cord Injury Pain Basic Dataset, version 2.0 (ISCIPIBDS2), which was developed by a team headed by [name],^{78, 79} and the Spinal Cord Injury Pain Inventory (SCIPI)⁸⁰, to identify pains that were likely to be neuropathic in nature. Of the 50 subjects interviewed, 41 (82%) reported having a persistent pain problem (at least 3 months in duration), and for 30 (60%) respondents, at least one of their pains was identified as neuropathic (based on location of the pain at- or below-the neurologically-determined level-of-injury and a SCIPI score of ≥ 2). This percentage is similar to a recent prospective study in the literature which found 59% of its participants had neuropathic pain at one year post-SCI.²¹

Relationships between Neuropathic pain and somatosensory function (quantitative sensory testing; QST)

We have utilized a number of psychophysical techniques to investigate the association between both DC-MLS- and STT-mediated function and the severity of chronic Neuropathic pain after SCI. We have shown (**Table 1**) that the test-retest reliability of threshold measures across most somatosensory submodalities in subjects

with SCI is substantial, and comparable, or superior to, the reliability of these measures in nondisabled control subjects. Hot and cold pain thresholds are more variable over time, but are still significantly related.

Thus, these measures are appropriate for assessing changes in sensory function across time, as proposed in this application. Several publications from our studies have linked heightened evoked pain sensitivity at- and below-the LOI (as measured with QST techniques including pain thresholds) and greater

Table 1: Test-retest reliability for thresholds in persons with SCI and NeuP compared to thresholds in nondisabled control subjects

[figure not shown]

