- We will use the components of the International SCI Pain Basic Data Set, version 2.0 (ISCI PBDS2),⁷⁹ to record the presence of pain, the interference of pain on activities of daily living, mood, and sleep, locations of pains, intensity of pain, the onset of the pain condition, and whether treatments are currently being used for the pain condition. The guidelines provided in the ISCI PBDS2 regarding diagnosis of pain will be used to classify each pain condition a subject reports. For each research subject at each full assessment session (baseline, end of treatment, and 12 months post-injury), two experienced SCI pain researchers (Drs. [name] and [name]) will evaluate the characteristics of each pain a subject has to make a determination of diagnosis. These characteristics will be taken from the ISCI PBDS2 and the International SCIPEDS questions and other assessments regarding pain characteristics (e.g., location relative to LOI, quality of pain) and sensory testing results (see “Quantitative Sensory Testing” section, below). If the two assessors differ with regard to diagnosis, review of data and evaluations will be discussed by the assessors and consensus will be reached. *These pain classifications will be used to compare with NeuP classification identified by a SCIP score of ≥2, and to evaluate relationships between different pain types and other variables measured [Aims 2].*
- We will use selected components from the newly-published International SCI Pain Extended Data Set (ISCI PEDS),⁹³ to record temporal characteristics of the pain (“How long does your pain usually last?”, and “When during the day is the pain most intense?”), as well as treatments the subject is using for pain (“treatments” section of the ISCI Pain Extended Data Set). For each treatment the subject can respond with regard to whether he/she is currently using the treatment, how often, the dose, and adverse effects, and his/her global impression of change⁹⁴ *Responses to the treatment*

section will be used as a supplemental assessment of pain severity⁹² [Aim 1]. Lower doses of pain treatments suggest lower pain severity, while higher doses suggest a greater need for pain relief/ higher pain severity.

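### Chronic neuropathic pain is defined as lasting three months or more, but the primary endpoint that claims to count it has no duration condition

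*Combined protocol and SAP*

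**What the plan says.** - **Definition.** Section 3 (Background) notes that studies use either three or six months, and chooses for this protocol: "we operationally define chronic neuropathic pain as neuropathic pain that has persisted for three months or more".
- **Endpoint.** Section 8 gives the first primary endpoint as "the percentage of subjects who develop chronic neuropathic pain at the 12-month post-spinal cord injury time point", defined by a SCIPI score of at least 2. It states no duration.
- **Scoring rule.** Section 11, Hypothesis 1a, counts as positive "Subjects who score a 2 or more on the SCIPPI for a pain located at or below their neurological level of injury" at the 12-month visit. Subjects with neuropathic symptoms before entry are positive if they have "neuropathic pain that is moderate or greater (rated at least a 4 out of 10) at the 12 month follow-up assessment". The first rule adds location and the second adds severity. Neither adds duration.
- **Data collected.** Section 9 has the ISCIPBDS2 record "the onset of the pain condition". Table 2 places the SCIPI and ISCIPBDS2 in the abbreviated assessment, which is given by phone each month after treatment until month 12. Nothing in the plan uses these items to apply the three-month definition to the primary endpoint.
- **Planning rate.** Section 11 projects 60% in the sham arm from two earlier sources. One is the in-house phone survey in section 3, in which 41 of 50 respondents "reported having a persistent pain problem (at least 3 months in duration") and 30 of 50 had at least one pain identified as neuropathic.

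**The concern.** The title, Aim 1, Hypothesis 1a, the power statement and the text on early action in section 12 all speak of chronic neuropathic pain. The scoring rule delivers a point prevalence of neuropathic pain at one visit. A subject whose first qualifying pain is two weeks old at month 12 is counted as having developed the chronic condition. Read literally, a subject with neuropathic pain before entry that stays at 3 out of 10 through month 12 is counted as negative, while a newcomer with a recent 1-out-of-10 pain that meets SCIPI and location is positive.

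Two things are at stake. A conclusion about chronic pain would rest on an endpoint that never tests chronicity by the protocol's own definition. And if recent pain behaves differently from established pain under TENS, the observed contrast would not be the contrast in chronic pain.

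**Working it through.** **1. Does anything supply the missing duration?**

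- Location at or below the level of injury: no.
- The 4-out-of-10 rule: no. These subjects enrol within four months of injury, so their first symptoms precede month 12 by at least 12 − 4 = 8 months. Continuity to month 12 is not required, however.
- The expert classification in sections 9 and 11: no. It concerns pain type, is used as confirmation, and states no three-month criterion.
- The pain rating over the past 3 months: no. It asks for average intensity, not how long the pain has lasted.

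**2. The plan's own power figure.** Inputs from section 11: 41 per arm, 60% v 30%, two-sided alpha 0.05, two-proportion z-test.

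Power = Φ[(d − 1.96·SE0)/SE1], where d = 0.60 − 0.30, SE0 = √(2·0.45·0.55/41) and SE1 = √((0.60·0.40 + 0.30·0.70)/41). This gives 79.0%; exact enumeration of the pooled z-test gives 81.3%. The plan says at least 80%, so the figure reproduces. The point concerns the endpoint definition, not this arithmetic.

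**3. Size, under stated assumptions.** The documents do not give the share s of sham positives whose pain began in the last three months. I assume s = 5%, 10% or 20%. The upper value is close to what even onset would give: section 9 says about 25% of one-year cases had symptoms at month 1, so (100% − 25%)/11 = 6.8% per month, and three months give 20.5%. I also assume that TENS halves established pain and leaves recent pain unaffected.

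With r = 60% × s:

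- Rule as written: sham 60%, TENS = r + (60% − r)/2.
- Three-month rule: sham 60% − r, TENS (60% − r)/2.

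| s | r (points) | As written | Apparent relative reduction | Power | Three-month rule | Power |
|---|---|---|---|---|---|---|
| 0% | 0 | 60% v 30% | 50% | 79.0% | 60% v 30% | 79.0% |
| 5% | 3 | 60% v 31.5% | 47.5% | 74.5% | 57% v 28.5% | 75.1% |
| 10% | 6 | 60% v 33% | 45% | 69.5% | 54% v 27% | 70.9% |
| 20% | 12 | 60% v 36% | 40% | 58.8% | 48% v 24% | 62.3% |

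The absolute difference is (60% − r)/2 under both rules: 28.5, 27 and 24 points. The three-month rule brings the relative reduction back to 50% but leaves the absolute difference unchanged. Power therefore gains only 0.6, 1.4 and 3.5 points.

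**4. Other assumptions.** If TENS halves all neuropathic pain, recent or not, the rule as written keeps 60% v 30% and 79.0% power, and the three-month rule lowers power to 75.1%, 70.9% or 62.3%. If the projected 60% already means pain of three months or more, adding the requirement leaves 60% v 30% and 79.0% unchanged.

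**The case against.** The strongest reply is that this is a matter of labelling. Section 8 gives its own explicit definition (SCIPI of at least 2), and the scoring rule in section 11 says positive for neuropathic pain without the word chronic. That stands in part: relabelling is an acceptable remedy. It does not remove the inconsistency, because section 8 still calls the endpoint chronic and section 3 says what chronic means here.

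Several stronger readings are tempting and are not supported:

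- *Recent onset must be common.* Section 3 says only that neuropathic pain often does not develop until at least a few months after injury. That is compatible with most onset before month 9.
- *The current rule costs material power, and the change restores it.* The table shows otherwise. Nothing in the documents says that late pain would escape TENS; the rationale is prevention of central sensitization and so of later pain.
- *The 60% planning rate was built on three-month pain.* In section 3 the three-month phrase attaches to the 41 with persistent pain. The 30 neuropathic cases are described by location and SCIPI score, as in the scoring rule. They may be a subset of the 41, but this is not said outright. The second source, 59% at one year, is cited without a duration rule. The planning rate and the endpoint may not match; no more can be said.
- *Any SCIPI-positive pain counts.* Location applies, as does the severity rule for subjects symptomatic before entry. For pain in that group that has persisted, the gap is largely moot.
- *The safety endpoint has the same defect.* It names chronic pain, not chronic neuropathic pain.

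Timing is also a fair objection. This version is dated July 2022, planned enrolment ended in January 2022, and section 12 plans between-group comparisons of the primary endpoints after every 20 completers. A new primary definition now is a late endpoint change, and the remedy has to allow for that.

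**Conclusion.** The inconsistency holds, with high confidence: the protocol defines chronic as three months or more, scores its chronic-pain endpoint without a duration, and nothing else supplies one. The size cannot be determined from the documents. If 5% to 20% of sham positives are recent-onset and TENS affects only established pain, the apparent relative reduction is 47.5% to 40% instead of 50%. Both conditions are assumptions. A reader might infer that the primary comparison is seriously diluted, or that correcting it rescues power; neither follows. The change is worth making because a conclusion about chronic pain needs an endpoint that measures it.

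**What to change.** **Preferred.** In section 8 and in section 11, Hypothesis 1a, count a subject as positive for chronic neuropathic pain only if the qualifying month-12 pain has an ISCIPBDS2 onset at least three months earlier. Use the monthly SCIPI results as supporting information only. Section 9 gives the SCIPI a sensitivity of 78%, so requiring repeated positives would drop true cases. Date the change, base it on the existing section 3 definition, make it without reference to between-group data, and report the duration-free count alongside.

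**Alternative**, if the sponsor prefers not to alter the primary definition this late. Keep the current count, label it point prevalence of neuropathic pain at 12 months, and add the three-month version as a prespecified sensitivity analysis on which any conclusion about chronic pain depends.

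**Cost.** No new visit or instrument is needed. The preferred route is nonetheless a documented change to a primary endpoint, not merely an edit of wording. It relies on recalled onset and may give a somewhat lower sham event rate, with the possible loss of power shown above.
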